Also, the large number of subjects enrolled will allow an opportunity to describe, as an exploratory objective, two different treatment durations in terms of safety, efficacy, and patient-reported outcomes (PRO) data. In study MDX1106-03, after 48 weeks of treatment with nivolumab at the 3 mg/kg dose level, 27% of the NSCLC subjects were still on treatment (95% CI: 12.7%, 41.3%). Following on that observation, in the current study, subjects who are still benefiting from the drug after completing 1 year of treatment will be randomized 1:1 in two cohorts. Subjects randomized to Cohort A will continue on treatment until progression, unacceptable toxicity, or withdrawal of informed consent. Subjects randomized to Cohort B will remain on study but will discontinue treatment. Upon disease progression, subjects in Cohort B will be allowed to resume treatment. Subjects randomized to Cohort B who restart treatment will then continue on treatment until progression, unacceptable toxicity, or withdrawal of informed consent.

An additional 500 subjects will be treated under Protocol Amendment 04 (December 2014) to continue collecting safety information and to characterize the outcome of immune-mediated side effects. These additional data will provide a larger data set to inform the risk/benefit profile of the use of nivolumab in lung cancer patients and will help to further clarify the effectiveness of the current treatment algorithms for managing drug- mediated toxicities (See [Appendix 2](#) for Management Algorithms).

1.1.2 *Rationale for Subject Subgroups*

Obtaining additional data on the incidence and outcome of high grade (Grade 3-4 and Grade 5) select events in a similar patient population as that included in the nivolumab registrational NSCLC studies is warranted to further support the assessment of risk/benefit.

Obtaining similar data in patient populations that have been previously excluded from the registrational studies (ie. subjects with PS 2) will provide critical information for the nivolumab clinical development program, and also for medical oncologists when making treatment decisions. Treatment with nivolumab in subjects with PS 2 is planned to allow for signal detection for both safety and efficacy as an exploratory objective (subgroup 4). This data will inform if further investigation of the risk/benefit profile of nivolumab in this subject subset is justified.

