3.5 Discontinuation of Subjects from Treatment

Subjects MUST discontinue investigational product (and non-investigational product at the discretion of the investigator) for any of the following reasons:

- Subject's request to stop study treatment
- Any clinical adverse event (AE), laboratory abnormality or intercurrent illness which, in the opinion of the investigator, indicates that continued participation in the study is not in the best interest of the subject
- Pregnancy
- Termination of the study by Bristol-Myers Squibb (BMS)
- Loss of ability to freely provide consent through imprisonment or involuntarily incarceration for treatment of either a psychiatric or physical (eg, infectious disease) illness
- After randomization in Cohort B, until disease progression when subjects are eligible for retreatment
- Other protocol specific reasons for discontinuation as specified in [Section 4.3.5](#).

All subjects who discontinue investigational product should comply with protocol specified follow-up procedures as outlined in [Section 5](#). Subjects in Cohort B continue with the on-study visit schedule ([Table 5.1-2](#)) until disease progression following retreatment or upon a decision to not receive retreatment, unacceptable toxicity, or withdrawal of informed consent. The only exception to this requirement is when a subject withdraws consent for all study procedures including post-treatment study follow-up or loses the ability to consent freely (ie, is imprisoned or involuntarily incarcerated for the treatment of either a psychiatric or physical illness).

If study treatment is discontinued prior to the subject's completion of the study, the reason for the discontinuation must be documented in the subject's medical records and entered on the appropriate case report form (CRF) page.

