LCSS and EQ-5D	X		X		
Complete every 3 cycles (every 6 weeks) on Day 1 during first 1 year (52 weeks) of treatment. After randomization at one year (52 weeks), every other cycle on Day 1.
 
Complete assessments prior to any contact with study staff if possible

^a Monitor amount of supplemental oxygen if applicable. If a subject shows changes in oxygen saturation or supplemental oxygen requirement, or other pulmonary-related signs (eg, hypoxia, fever) or symptoms (eg, dyspnea, cough) consistent with possible pulmonary adverse events, immediately evaluate to rule out pulmonary toxicity, according to the suspected pulmonary toxicity management algorithm provided in the Investigators' Brochure.

^b Review serum chemistry and liver function prior to dosing. Perform CBCs prior to dosing but results need not be reviewed prior to dosing.

Table 5.1-3: Follow-up Procedural Outline (CA209153)

Procedure	Initial Follow-Up Phase (100 days from the date of last study treatment) Follow-up Visit 1 (X01) and Visit 2 (X02)	Further Follow-up Phase (beyond X02)	Notes 
 • Subjects who discontinue treatment prior to randomization and subjects in Cohort A: Follow-up Visit 1 (X01) is to occur 30 days (\pm 5 days) after last dose or coinciding with the date of discontinuation (\pm 5 days) if date of discontinuation is greater than 35 days after last dose. • Subjects in Cohort B: Follow-up Visit 1 (X01 is to occur 30 days (\pm 5 days) after disease progression and a decision has been made to not retreat the subject or at 30 days (\pm 5 days) of discontinuation after retreatment • Follow up Visit 2 (X02) is to occur approximately 70 days (\pm 5 days) after X01
Radiographic Tumor Assessment	X	X	For subjects who discontinue study treatment for reasons other than PD, follow up scans (or MRIs when appropriate) should be performed every 8 weeks (\pm 5 days) up to 24 months from first dose then every 12 weeks (\pm 5 days) until PD, death, lost to follow-up, or withdrawal of consent; radiographic assessments should not delayed until the X01 or X02. After 24 months of treatment, the frequency of surveillance brain MRI or CT scans will be every 6 months or earlier, if clinically indicated for subjects with known brain metastases.
Safety Assessments			
Vital Signs	X		
Physical measurements	X		Includes performance status (ECOG)

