Adverse Events Assessment	X	X	*Beyond 100 days from the last dose of study therapy, subjects will be followed for ongoing drug-related AEs until resolved, return to baseline or deemed irreversible, or until lost to follow-up or withdrawal of study consent.

Table 5.1-3: Follow-up Procedural Outline (CA209153)

Procedure	Initial Follow-Up Phase (100 days from the date of last study treatment) Follow-up Visit 1 (X01) and Visit 2 (X02)	Further Follow-up Phase (beyond X02)	Notes 
 • Subjects who discontinue treatment prior to randomization and subjects in Cohort A: Follow-up Visit 1 (X01) is to occur 30 days (\pm 5 days) after last dose or coinciding with the date of discontinuation (\pm 5 days) if date of discontinuation is greater than 35 days after last dose. • Subjects in Cohort B: Follow-up Visit 1 (X01) is to occur 30 days (\pm 5 days) after disease progression and a decision has been made to not retreat the subject or at 30 days (\pm 5 days) of discontinuation after retreatment • Follow up Visit 2 (X02) is to occur approximately 70 days (\pm 5 days) after X01
Laboratory Tests	X		CBC with differential, serum chemistry (BUN or serum urea level, serum creatinine, albumin, sodium, potassium, calcium, magnesium, phosphate, chloride, glucose), liver function (AST, ALT, total bilirubin, alkaline phosphatase, LDH), thyroid function (TSH, reflex to free T3 and free T4 if abnormal result)
Review of concomitant medications	X		
Pregnancy testing	X		
EQ-5D	X	X	Beyond 100 days from the last dose of study therapy, the EQ-5D will be administered every 3 months for the first 12 months, then every 6 months thereafter, as permitted by local IRB
Collection of Survival Information	X	X	Every 3 months until death, lost to follow-up, or withdrawal of study consent for 5 years following start of therapy. May be performed by phone contact or office visit.

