5.2 Study Materials

The following materials will be provided at study start:

- NCI CTCAE version 4.0
- BMS-936558 (nivolumab) Investigational Brochure
- Pharmacy Binder
- Laboratory manuals for collection and handling of blood [REDACTED] and tissue specimens
- Site manual for operation of interactive voice response system (for study enrollment)
- Serious Adverse Event (or eSAE) case report forms
- Pregnancy Surveillance Forms
- RECIST 1.1 pocket guide
- PRO manual

Each site will be provided with PRO questionnaires. Subjects will complete these at the time of the scheduled visits, prior to any study procedures and study drug infusion. During the survival follow-up period beyond X02, the EQ-5D PRO will be administered at a frequency of every 3 months for the first 12 months, then every 6 months thereafter, as permitted by local law. (see schedule [Table 5.1-2](#) and [Table 5.1-3](#) for frequency of assessments).

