5.7 Outcomes Research Assessments

Patient reported outcomes (PRO) will be measured according to Table 5.1-2 and Table 5.1-3, using the following two validated subject self-reported questionnaires: Lung Cancer Symptom Scale (LCSS), and EuroQOL Group's EQ-5D.

Subjects will be asked to complete questionnaires before any clinical activities are performed during visits to the study clinics at on-study visits, and at the designated study visits in the follow-up (post-treatment) phase of the study.

Questionnaires will be provided in the subject's preferred language.

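### After week 52, LCSS stays scheduled for Cohort B subjects who are off drug but not for Cohort A subjects who stop nivolumab, so the by-cohort LCSS summaries rest on differently selected subjects

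*Combined protocol and SAP*

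**What the plan says.** Section 1.1.1 gives as an exploratory aim the description of "two different treatment durations in terms of safety, efficacy, and patient-reported outcomes (PRO) data". Cohort A continues nivolumab after week 52. Cohort B stops and may be retreated at progression.

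- **On-study schedule.** The LCSS and EQ-5D row of Table 5.1-2 changes the frequency once subjects are randomised: "After randomization at one year (52 weeks), every other cycle on Day 1".
- **Cohort B off drug.** Section 3.5: "Subjects in Cohort B continue with the on-study visit schedule". This lasts until progression after retreatment, a decision against retreatment, unacceptable toxicity or withdrawal of consent. The header of Table 5.1-3 agrees: Cohort B reaches its first follow-up visit 30 days "after disease progression and a decision has been made to not retreat the subject", or 30 days after stopping retreatment.
- **Cohort A off drug.** The same header: "Subjects who discontinue treatment prior to randomization and subjects in Cohort A: Follow-up Visit 1 (X01) is to occur 30 days" after the last dose, or at the date of discontinuation if that is more than 35 days after the last dose. The reason for stopping does not matter.
- **Follow-up schedule.** Table 5.1-3 has an EQ-5D row (X01 and X02, after which "the EQ-5D will be administered every 3 months for the first 12 months, then every 6 months thereafter") and no LCSS row. Section 5.2 likewise names one instrument: "During the survival follow-up period beyond X02, the EQ-5D PRO will be administered at a frequency of every 3 months".
- **Analysis.** Section 8.4.4.3 summarises change from baseline in both instruments at each assessment point, including for randomised Cohorts A and B. It defines LCSS completion as forms received over forms expected and gives no rule for LCSS that is no longer scheduled.

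**The concern.** Two randomised subjects can be in the same state, off drug and progression-free, yet one is asked for LCSS every 4 weeks and the other is never asked again. Whether a Cohort A subject keeps giving LCSS depends on staying on nivolumab, and staying on treatment is part of what the duration comparison is about. At a given time point after week 52, Cohort A's LCSS summary comes from subjects still on treatment. Cohort B's comes from subjects on or off drug, including some who have progressed and been retreated.

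This is the study's only randomised comparison, and patient-reported outcomes are a named part of it. Randomisation made the cohorts comparable at week 52. Measurement that depends on later dosing in one cohort and not in the other gives that up for LCSS.

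**Working it through.** **1. The plan's own figure.** Section 8.1.1 expects 99 to 322 randomised subjects. The source is 10 of 37, with a Wald interval:

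0.2703 ± 1.96 × √(0.2703 × 0.7297 / 37) = 12.7% to 41.3%

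Times 780 this gives 99.1 to 322.1, so the range reproduces; it means about 50 to 161 per cohort. At the current total of 1280 treated, the same rates give 163 to 529, or about 81 to 264 per cohort.

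**2. Scheduled forms in the 52 weeks after randomisation.** Every other 14-day cycle is 4 weeks, so a subject who stays on Table 5.1-2 has 52 / 4 = 13 forms of each instrument. This treats cycles as calendar periods for Cohort B subjects off drug. For Cohort A, X01 is 30 days after the last dose, X02 is 70 days after X01, and EQ-5D then follows about every 91 days.

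| Subject | LCSS to last dose | LCSS afterwards | EQ-5D afterwards |
|---|---|---|---|
| Cohort B, off drug, no progression | – | 13 of 13 | 13 |
| Cohort A, last dose week 8 after randomisation | 2 | 0 (Cohort B: 11) | 4 (Cohort B: 11) |
| Cohort A, last dose week 16 | 4 | 0 (Cohort B: 9) | 3 (Cohort B: 9) |
| Cohort A, last dose week 26 | 6 | 0 (Cohort B: 7) | 2 (Cohort B: 7) |

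Cohort A's follow-up EQ-5D is timed from the last dose, not from randomisation. With a last dose at day 56 the forms fall on days 86, 156, 247 and 338. Day 86 is close to Cohort B's day 84, but day 156 is 12 days from the nearest Cohort B form (day 168). The two calendars meet only by chance.

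**3. What the completion rate shows.** If expected means scheduled, the week-8 stopper has 2 received of 2 expected, or 100%. Against the 13 forms of the common calendar it is 2 / 13 = 15%. The planned statistic cannot show the gap.

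**4. Size, by assumption only.** If a share d of Cohort A stops and would have scored D standard deviations worse than the rest, the observed mean is too favourable by d × D. The documents give neither quantity. Assuming d = 5% to 20% and D = 0.3 to 0.8:

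- shift: 0.05 × 0.3 = 0.015 SD up to 0.20 × 0.8 = 0.16 SD
- subjects without later LCSS: about 2 to 32 on the 780 base, 4 to 53 on the 1280 base

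If stoppers score better than the rest, the sign reverses.

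**The case against.** **Other text might restore LCSS.** Section 5.7 has subjects complete questionnaires at on-study visits "and at the designated study visits in the follow-up (post-treatment) phase of the study". It refers to the two tables for what is due, and Table 5.1-3 designates only EQ-5D. Section 5.3.2 tells subjects who stop for toxicity to follow the procedures of the last on-treatment visit, from either table. Part of that passage is blacked out. What can be read sets no continuing LCSS schedule, but the sponsor should confirm this. The PRO manual listed in Section 5.2 is not available to us.

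**Stronger readings that the documents do not support.**
- *A reader might infer that the whole PRO comparison loses Cohort A's intolerant subjects.* It does not. EQ-5D continues in follow-up, and LCSS completed before stopping still counts.
- *A reader might infer that Cohort B has no comparable loss.* It has: LCSS also ends there when retreatment is declined or stopped. The cohorts differ in when and for whom LCSS ends.
- *A reader might infer a bias in favour of continued treatment.* That needs Cohort A stoppers to score worse. The plan uses LCSS for disease-related symptoms, and someone who stops without progression may still have controlled disease. In the Phase 1 study, 9 of the 10 subjects still on treatment at one year had durable responses (Section 1.1.2.1). Progressed subjects also enter differently: Cohort B keeps them through retreatment and loses those who decline it; Cohort A keeps only those treated beyond progression. The net direction is unknown.

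**The stakes are limited.** The comparison is exploratory and descriptive, with no stated PRO test, power or decision rule. That is right, and it limits the consequence to interpretation. It does not remove the point, because unadjusted means by cohort show the effect of selective measurement directly.

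**Conclusion.** The point holds for LCSS. After week 52 it is scheduled every 4 weeks for Cohort B subjects off drug and through retreatment, and is no longer scheduled for Cohort A subjects once they stop nivolumab for any reason. For EQ-5D the weakness is smaller: fewer forms, on a different clock. The schedule difference is certain from the visible text and rests on no assumption, apart from what the blacked-out part of Section 5.3.2 may contain.

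The effect on the cohort means cannot be signed or sized from the documents. The 0.015 to 0.16 SD above is an illustration under assumed inputs, not an estimate. As planned, the by-cohort LCSS summaries should not be read as a comparison of the randomised groups, and a high completion rate should not be taken as reassurance. The change is worth making, but it does not touch the primary or secondary objectives.

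**What to change.** 1. **Schedule.** Add LCSS to Table 5.1-3 for randomised subjects. Collect LCSS and EQ-5D in both cohorts on one post-randomisation calendar regardless of dosing, using X01, X02 and the scan visits that Table 5.1-3 already requires for subjects who stop without progression. Scans fall 8, 16, … weeks after first dose, so nominally at weeks 56, 64, 72, 80, 88, 96 and 104. That is 4, 12, 20, 28, 36, 44 and 52 weeks after randomisation: seven points in the first year, all on the 4-weekly grid. The later 12-week interval is also a multiple of 4. Scans end at progression, so for progressed subjects the existing contacts are X01, X02 and the later EQ-5D follow-up. State which of these carry LCSS.

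2. **Analysis.** In Section 8.4.4.3, summarise the cohorts at the common time points over all randomised subjects with data, on or off drug. A summary restricted to progression-free subjects conditions on an outcome that treatment duration may affect, so keep it supplementary.

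3. **Data already missed.** By cohort and time point, report the number of randomised subjects alive and in follow-up without LCSS, split into off drug without progression, progressed, and form not returned. Do not rely on completion against expected forms alone.

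4. **Text.** Reconcile Sections 5.3.2 and 5.7 with Table 5.1-3.

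The cost is one table row, some analysis wording, and a short extra questionnaire for a limited number of subjects, mostly at existing visits. The current protocol is dated December 2017 and the last enrolment expansion December 2014, so much of the relevant period may have passed before a schedule change takes effect. Items 2 and 3 need no new data and can be settled before the final analysis, which waits for five-year follow-up.

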Radiographic Tumor Assessment (Chest, Abdomen, Head)	X	Within 28 days prior to first dose. CT/MRI of brain (with contrast, unless contraindicated) required for subjects who have known history of brain metastases or if clinically indicated.. Additional sites of known or suspected disease (including pelvis) should be imaged at the screening visit.
Archived Tumor Tissue or Recent Tumor Biopsy	X	
One formalin-fixed paraffin embedded tumor tissue block, or 10 minimum FFPE unstained slides are to be submitted if available. Submit a copy of the original pathology report along with the sample. Tissue samples from different biopsy procedures are to be submitted if available with each matching pathology report and biopsy date.
 
NOTE: For subjects previously enrolled in CA 209118, tumor tissue and/or laboratory data generated from tissue collected in CA209118 is to be utilized for this study.

Table 5.1-2: On-Study Procedural Outline (CA209153)

Procedure	C1D1 (Cycle 1 Day 1)	Each Cycle (Every 2 weeks) on Day 1	Every 3 Cycles (Every 6 weeks) on Day 1	Every 4 Cycles (Every 8 weeks) on Day 1	Notes
Safety Assessments					
Vital Signs and oxygen saturation ^a	X	X			Within 72 hours prior to dosing. Include temperature, blood pressure, heart rate, respiratory rate, oxygen saturation by pulse oximetry at rest prior to dosing and at any time there are new or worsening respiratory symptoms. (see Section 5.3.2) Patients randomized to Cohort B will be assessed every 2 or 4 weeks for clinical assessment and physical examination per investigator decision. If nivolumab is restarted, every two week assessment schedule must be resumed.
Adverse Events Assessment			Continuously		Continuously assessed using NCI CTCAE v. 4.0.
Physical measurements and target physical exam (including Performance Status)	X	X			Includes weight, ECOG status, and targeted physical exam as clinically indicated Patients randomized to Cohort B will be assessed every 2 or 4 weeks for clinical assessment and physical examination per investigator decision. If nivolumab is restarted, every two week assessment schedule must be resumed.
Laboratory Tests^b					Cohort B: For subjects randomized to Cohort B, lab tests will be performed every 4 weeks. If nivolumab is restarted, every two week lab assessment schedule must be resumed.

Table 5.1-2: On-Study Procedural Outline (CA209153)

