Descriptive statistics of safety (AE and lab data) including incidence, median values using the Kaplan-Meier (KM) product-limit method with 95% CI using Brookmeyer and Crowley method of time to onset and time to resolution, and rate of discontinuation due to event occurrence will be presented for all treated subjects, by tumor histology (SQ or NSQ), by subject subgroups, and all randomized subjects for Cohorts A and B. Time to onset is calculated from first dosing date to the event onset date. If a subject never experienced the given AE, the subject will be censored at the last contact date. Time to resolution is calculated from the AE onset date to AE end date. If an AE is ongoing at the time of analysis, the time to resolution will be censored at the last contact date.

8.4.4.2 *Efficacy Analyses*

[figure not shown]
OS and PFS will be summarized by KM product-limit method for all treated subjects and all response evaluable subjects, respectively. Median values of OS and PFS, along with two-sided 95% CI using Brookmeyer and Crowley method, will be calculated. Survival rates at 6, 12, 18 and 24 months will also be estimated using KM estimates on the OS curve for all treated subjects. Associated two-sided 95% CIs will be calculated using the Greenwood formula. This analysis will be performed for all treated subjects or for all response evaluable subjects for PFS. This analysis will also be performed by tumor histology (SQ or NSQ), by subject subgroups, and all randomized subjects for Cohorts A and B.

The ORR will be summarized by binomial response rates and their corresponding two-sided 95% exact CIs using the Clopper-Pearson method. This analysis will be performed for all response evaluable subjects. This analysis will also be performed by tumor histology (SQ or NSQ), by subject subgroups, and all randomized subjects for Cohorts A and B.

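### AE and laboratory collection windows differ between randomised Cohorts A and B, and Section 8.4.4.1 sets no common window or person-time basis, so the A v B safety summaries are not on the same footing

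*Combined protocol and SAP*

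**What the plan says.** Three parts of the protocol set the collection window.

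- **Start of follow-up (Table 5.1-3, Notes).** For Cohort A, and for subjects who stop before randomisation, X01 is 30 days "after last dose or coinciding with the date of discontinuation" if that date is more than 35 days after last dose. For Cohort B, X01 is 30 days "after disease progression and a decision has been made to not retreat the subject or at 30 days" from discontinuation after retreatment. In both cohorts, "Follow up Visit 2 (X02) is to occur approximately 70 days" after X01.
- **Off-drug time in Cohort B (Section 3.5, Table 5.1-2).** "Subjects in Cohort B continue with the on-study visit schedule", where AEs are "Continuously assessed using NCI CTCAE v. 4.0" and labs are drawn every 4 weeks.
- **After X02 (Table 5.1-3).** No labs, vital signs or concomitant-medication review are scheduled. The AE row stays marked, but its note narrows: "Beyond 100 days from the last dose of study therapy, subjects will be followed for ongoing drug-related AEs until resolved". Tumour scans continue every 8, later 12, weeks until progression in subjects who stopped for another reason.

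Section 8.4.4.1 summarises on-study AEs and labs without defining that period in days. It then presents "Descriptive statistics of safety (AE and lab data) including incidence, median values" of time to onset and time to resolution, among other breakdowns, for randomised Cohorts A and B. Subjects without the event are censored at last contact.

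**The concern.** Two subjects can both be off nivolumab and progression-free, yet be observed differently only because of their randomised cohort. The Cohort B subject is asked about all AEs and has blood drawn every 4 weeks. The Cohort A subject, once past X02, has no scheduled labs and no clear provision for recording a new non-serious AE.

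This is the trial's only randomised contrast. Describing the safety of the two treatment durations is a stated exploratory aim (Sections 1.1.1 and 1.3.3). A crude percentage with no person-time denominator cannot separate fewer events from less looking. Censoring at last contact adds to the problem: survival contacts run every 3 months for 5 years from start of therapy, so a Cohort A subject can contribute years of apparently event-free time in which new non-serious AEs were not being sought.

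**Working it through.** **1. The 100 days.** X01 at day 30 plus 70 days gives X02 at day 100 after last dose. With ±5 days at each visit the range is 90 to 110. This reproduces the column header, "Initial Follow-Up Phase (100 days from the date of last study treatment". If discontinuation is declared later than day 35, X02 moves out accordingly; for example, 42 + 70 = day 112 after a 6-week interruption.

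**2. The same clock in Cohort B.** Take a subject who stops at week 52, progresses 365 days later and is not retreated. X01 is at day 365 + 30 = 395 and X02 at 395 + 70 = 465 after last dose, against about 100 in Cohort A. Scheduled lab visits in that off-drug year are 52/4 = 13 in Cohort B, against 2 (X01 and X02) for a Cohort A subject who has stopped.

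**3. Effect on one event type.** Assume a new event that is not reportable after day 100, a constant hazard h per year, and one progression-free year off drug. The proportion captured is 1 − exp(−h × 100/365.25) in Cohort A and 1 − exp(−h) in Cohort B.

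| h per year (assumed) | Cohort A | Cohort B |
|---|---|---|
| 0.05 | 1.4% | 4.9% |
| 0.10 | 2.7% | 9.5% |
| 0.30 | 7.9% | 25.9% |

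**4. Share of Cohort A time affected.** The documents give no rate of stopping before progression, so the annual proportion q is an assumption shown as a range.

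- Time from randomisation to progression: exponential with p = ln 2/74 = 0.00937 per week. The 74 weeks is borrowed from the median duration of response in Section 1.4.3.3.
- Horizon H = 208 weeks (4 years from randomisation, Section 3.2).
- Time to stopping: exponential with d = −ln(1 − q)/52 per week.
- Collection lag c = 100/7 = 14.29 weeks.

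Mean pre-progression time is (1 − exp(−pH))/p = 91.5 weeks. Mean time past the lag is [exp(−pc) − exp(−pH)]/p − exp(dc) × [exp(−(p+d)c) − exp(−(p+d)H)]/(p+d).

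| q per year (assumed) | Weeks past day 100 | Share of 91.5 weeks |
|---|---|---|
| 5% | 5.05 | 5.5% |
| 10% | 9.84 | 10.8% |
| 15% | 14.38 | 15.7% |
| 20% | 18.67 | 20.4% |

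At q = 10%, a median of 52 weeks gives 8.9% and 104 weeks gives 12.2%. Over a one-year horizon, with medians of 12 to 36 months and q from 5% to 30%, the share is only 1% to 8%.

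**5. Time is not events.** At q = 10%, if the event hazard after day 100 is r times the earlier hazard, the share of events lost is 9.84r/(91.54 − 9.84 + 9.84r). That is 2.9% for r = 0.25, 5.7% for r = 0.5 and 10.8% for r = 1.

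**6. The opposite pull.** While on drug, Cohort A has labs every 2 weeks (52/2 = 26 per year) against 13 in off-drug Cohort B, and thyroid tests every 6 weeks (about 9 per year) against every 12 (about 4).

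**The case against.** A reader might infer that AE collection stops at day 100 in Cohort A, that nothing is lost in Cohort B, and that continuous treatment is therefore made to look safer. The documents do not support any of the three.

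- **Collection does not simply stop.** Related SAEs stay reportable without time limit (Section 6.1.1). Ongoing drug-related AEs are followed to resolution. Section 3.6 refers to following select AEs beyond 100 days, although it is unclear whether new ones count. Section 6.2.1 gives non-serious AE collection a start but no end. What is exposed is new non-serious AEs, unrelated SAEs and labs; serious related events are least affected.
- **Cohort B is not cleanly complete.** The 100-day header and AE note in Table 5.1-3 and the SAE window in Section 6.1.1 carry no Cohort B exception. Read literally, they restrict Cohort B from 100 days after its week-52 stop, which conflicts with Section 3.5.
- **The net direction is open.** More frequent testing of on-drug Cohort A raises detection there. It does not recover events missed after stopping, but it prevents a claim about the overall sign.

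Three further points stand. Section 5.3.2's instruction for subjects who stop for toxicity points to either schedule and is partly redacted, so it cannot be relied on either way. The asymmetry concerns Cohort B's first off-drug period only, because after retreatment X01 is again tied to discontinuation. The comparison is exploratory and descriptive, and the primary estimate in all treated subjects is not an A v B contrast. A single analysis window from last dose would remove the surplus Cohort B time, but the plan does not specify one.

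**Conclusion.** The concern holds in limited form. The schedules give the randomised cohorts different windows for new non-serious AEs and labs, and Section 8.4.4.1 neither defines a common window nor uses person-time. Followed as written, the A v B safety summaries are not comparable.

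Taken alone, this mechanism under-counts Cohort A. Its size is about 5% to 20% of Cohort A's pre-progression time for assumed stopping rates of 5% to 20% per year. That rests on exponential times, a borrowed 74-week median that describes responders rather than subjects randomised at week 52, a 4-year horizon, and full collection in Cohort B while off drug. It measures time, not events, and the share of events lost would be smaller if risk falls after stopping. Nor do the documents show that those who stop early in Cohort A do so mainly for toxicity. This is an inexpensive improvement to an exploratory summary and does not threaten the primary analysis.

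**What to change.** **In Section 8.4.4.1, for Cohorts A and B:**

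1. Count events from randomisation, and report incidence per person-year of actual AE collection time (and, separately, lab collection time) next to the crude percentages.
2. Show the period to first progression separately from the retreatment or post-progression period. Do not discard the latter: cutting at first progression would drop retreatment toxicity, which belongs to the Cohort B strategy.
3. Censor time to onset at the end of AE collection, not at last contact.
4. State the remaining differences in ascertainment and in lab frequency.

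**In the protocol text:** reconcile Sections 3.5, 3.6 and 6.1.1 and Table 5.1-3 on when AE collection ends in each cohort, and say whether new select AEs are recorded after day 100.

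**Cost.** The analysis changes need a few lines of text and an extra table, with no new patients or procedures.

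**Optional, if an amendment is still feasible:** ask about new AEs at the tumour-scan visits already required for Cohort A subjects who stop before progression. This needs IRB/IEC approval and adds site data entry, plus contact with study staff if scans are done away from the clinic. Lab windows would still differ, so it supplements the analysis changes and does not replace them.
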